**Cohorts**

Number	Name	Description
1	Cohort 1	Patients with HPV 16 positive vulvar HSIL enrolled to determine the MTD
2	Cohort 2	Patients with HPV 16 positive vulvar HSIL enrolled after MTD is determined

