### 3.1.3 E6 TCR T cell preparation

After cells are obtained by apheresis, further cell processing to generate E6 TCR cells will occur in the DTM according to standard operating procedures and the E6 TCR investigational new drug application. E6 TCR cells can be produced in approximately 21 to 27 days. Cell products may be cryopreserved during production to accommodate patient treatment schedules. Either freshly-collected cells or cryopreserved cells can be used to initiate the cell-preparation process. Peripheral blood mononuclear cells (PBMC) will be isolated. Sufficient cells for three complete cell productions (2-3 vials at  $3-4.5 \times 10^9$  cells/vial) will be retained in the DTM; the remaining cells will first be frozen in 10 vials at  $100 \times 10^6$  cells per vial with excess frozen at  $300 \times 10^6$  cells/vial. Cells will be frozen in the DTM and then transferred to ETIB the following day. Contacts in the ETIB preclinical core are [name] and [name] [contact]).

Before infusion, the percentage of T cells expressing the E6 TCR will be determined by flow cytometry. Successful TCR gene transfer will be defined as greater than 20% TCR positive cells. In addition to flow cytometry, further testing of the cells will take place prior to infusion to evaluate for microbial contamination, replication-competent retroviruses, and viability. Details of this testing can be found in the appropriate DTM SOPs. Any remaining pretreatment PBMC collected on this protocol and cryopreserved as described in Section 3.1.2 will be transferred from the Department of Transfusion Medicine to the Principal Investigator of this protocol for storage in the ETIB preclinical core and possible use in research and banked according to protocol 16-C-0061 (ETIB Tissue Procurement Protocol).

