### 3.1.5 Dose Limiting Toxicities (DLTs)

All treatment related Grade 3 and greater AEs occurring within 30 days of the cell infusion will be considered DLTs with the exception of the following expected transient effects of aldesleukin.

- Grade 3 fever or chills responsive to symptomatic treatment that resolve to  $\leq$  grade 2 in 48 hours.
- Grade 3 hypotension or oliguria responsive to  $\leq$  1.5L of IV fluid boluses in 24 hours that resolves to  $\leq$  grade 2 in 48 hours.
- Grade 3 dyspnea/hypoxia that improves to  $\leq$  grade 2 or less with supplemental oxygen and resolves to  $\leq$  grade 2 without supplemental oxygen in 48 hours.
- Grade 3 creatinine or electrolyte abnormalities that resolve to  $\leq$  grade 2 in 48 hours.
- Grade 3 or higher white blood cell count decreased and/or lymphocyte count decreased that resolves to  $\leq$  grade 2 in 72 hours.

Further outline of expected AEs with aldesleukin and their management is included in [Appendix B](#) and [Appendix C](#).

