### 3.1.6 Dose Escalation

The protocol will follow a 3+3 phase 1 dose escalation design. Three patients will be treated initially on dose level -1. If 2 of these 3 patients experience DLTs, the study will be stopped. If none of the 3 patients experiences a DLT, enrollment can start on dose level 1. If 1 of the first 3 patients experiences a DLT on dose level -1, 3 more patients will be treated at that dose level. If a second patient of the 6 has a DLT, the study will be stopped; otherwise, accrual can proceed to dose level 1. On dose level 1, if 2 patients have DLTs at any time during the treatment of 6 patients, then treatment on dose level 1 will be stopped, and 3 additional patients will be accrued at dose level -1 to reach a total of 6, if only 3 were previously treated. The maximum tolerated dose is the highest dose at which a maximum of 1 of 6 patients has a DLT.

There will be a minimum of a 7-day delay in treatment between the patients and a minimum of a 14-day delay in treatment between cohorts.

The total number of E6 TCR T cells transferred for each cohort will be:

- **Dose level -1**  $0.7 \times 10^{10}$  transduced T cells
- **Dose level 1**  $0.7 \times 10^{11}$  transduced T cells

The cell dose administered will be in a range of +/- 30% of the target dose above. The frequency of transduced T cells will be determined by flow cytometry with anti-mouse TCR beta-chain antibody. The number of transduced cells to be administered will be determined by multiplying the frequency of transduced T cells by the total number of viable T cells. If fewer than the target number of cells are generated the patient will be treated but toxicity data from the patient will not be used in determining the MTD, and that patient will be replaced in the protocol enrollment.

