### 7.5 DATA AND SAFETY MONITORING PLAN

#### 7.5.1 Principal Investigator/Research Team

The clinical research team will meet on a regular biweekly basis when patients are being actively treated on the trial to discuss each patient. Decisions about dose level enrollment and dose escalation if applicable will be made based on the toxicity data from prior patients.

All data will be collected in a timely manner and reviewed by the principal investigator. Adverse events will be reported as required above. Any safety concerns, new information that might affect either the ethical and or scientific conduct of the trial, or protocol deviations will be immediately reported to the IRB using iRIS.

The principal investigator will review adverse event and response data on each patient to ensure safety and data accuracy. The principal investigator will personally conduct or supervise the investigation and provide appropriate delegation of responsibilities to other members of the research staff.

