## 8 STATISTICAL CONSIDERATIONS

The primary objective of this phase I trial is to determine the safe dose level of E6 TCR T cells for the treatment of vulvar HSIL. Secondary objectives include an assessment of the clinical responses in subjects receiving this treatment and exploratory analyses of translational research endpoints.

This is a phase I trial with a standard 3+3 design and two dose levels. The maximum number of patients required to determine the MTD on this trial is 12. Six additional patients will be evaluated at the MTD, for a maximum intended enrollment of 18 patients. To allow for patients who enroll but are not evaluable for the primary endpoint and screen failures, up to 200 patients total may be enrolled.

The expected accrual rate is 10-15 patients per year. It should therefore take 1.25-2 years to complete accrual of patients.

The clinical responses in 12 patients tested at the MTD may be used in the design of a subsequent phase II trial.

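### DLTs are counted over 30 days, but the tenfold dose escalation may begin 14 days after the last infusion, before the window has closed

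*Combined protocol and SAP*

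**What the plan says.** Section 3.1.5 defines the toxicity window: treatment-related events of grade 3 or worse "occurring within 30 days of the cell infusion will be considered DLTs", apart from listed transient aldesleukin effects.

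Section 3.1.6 gives the decision rule: "If none of the 3 patients experiences a DLT, enrollment can start on dose level 1". If one of the first three has a DLT, three more are treated at level -1, and accrual moves up unless a second of the six has one. The step is from 0.7 x 10^10 to 0.7 x 10^11 transduced T cells. The section gives two waiting times, both minimums: 7 days between patients, and "a minimum of a 14-day delay in treatment between cohorts". It lists cell doses by cohort, so I read cohort there as dose level.

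The MTD is defined in the same section: "The maximum tolerated dose is the highest dose at which a maximum of 1 of 6 patients has a DLT". Cohort 2 (section 2.3.1) consists of "Patients with HPV 16 positive vulvar HSIL enrolled after MTD is determined".

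On what evidence the decisions rest, section 7.5.1 says: "Decisions about dose level enrollment and dose escalation if applicable will be made based on the toxicity data from prior patients". It gives no length of follow-up, and sections 3.1.7, 7.5.3 and 8 do not supply one.

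**The concern.** A 3+3 rule works as designed only if each patient counted as free of DLT has been watched for the period over which DLTs are defined. Here the waiting time is about half the DLT window. A team that keeps to the stated 14-day minimum can pass the 0-of-3 test on unfinished data.

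A DLT that appeared later in the window would have called for three more patients at level -1. By then a patient may already have received ten times the cell dose, which cannot be withdrawn. Section 3.1.6 does not say what happens to level 1 in that case. A single late, non-fatal DLT at level -1 also meets none of the stopping rules in section 3.1.7, which need a death, two affected patients, or two DLTs on level 1.

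The same gap leaves it unclear when the MTD, the primary result, is settled and Cohort 2 may open.

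**Working it through.** **Plan's own figures.** Two dose levels x 6 = 12 patients to find the MTD, and 12 + 6 = 18 in all, as section 8 states. The plan gives no figure for completed follow-up at a dose decision.

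**Inputs.** DLT window 30 days (3.1.5). Minimum gaps 7 and 14 days (3.1.6). Dose ratio 0.7 x 10^11 / 0.7 x 10^10 = 10. Section 8: "The expected accrual rate is 10-15 patients per year", so even gaps are 365/15 = 24.3 days or 365/10 = 36.5 days.

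**Follow-up at the decision.** Each patient's follow-up is the day of the next level's first infusion minus the patient's own infusion day. Window-days are capped at 30 per patient.

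- Three patients, fastest: infusions on days 0, 7, 14; next level on day 14 + 14 = 28. Follow-up is 28, 21, 14 days. None of 3 is complete; 63 of 90 window-days (70%).
- Six patients, fastest: days 0 to 35 in steps of 7; next step on day 49. Follow-up is 49, 42, 35, 28, 21, 14. Three of 6 are incomplete; 30 + 30 + 30 + 28 + 21 + 14 = 153 of 180 (85%). It is still three of 6 if 14 or 30 days separate the two groups of three.
- 15 per year, even gaps: 73.0, 48.7, 24.3 days. Two of 3 complete (84.3 of 90); five of 6 complete (174.3 of 180).
- 10 per year, even gaps: 109.5, 73.0, 36.5 days. All complete.

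**Effect on the rule (illustration).** The documents give neither a DLT rate nor an onset pattern. I assume a true 30-day rate p = 0.30 and two patterns for F(t), the share of DLTs that have occurred by day t (F = 1 from day 30):

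- early: F(t) = 0.8 + 0.2(t - 3)/27 for t of at least 3 days;
- uniform: F(t) = t/30.

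P(0/3 seen) = product over patients of [1 - p F(t)]. With complete follow-up this is 0.7^3 = 0.343. At the fastest spacing:

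- early: 0.704 x 0.720 x 0.736 = 0.373;
- uniform: 0.72 x 0.79 x 0.86 = 0.489.

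P(at least one later DLT given 0/3 seen) = 1 - 0.343 / P(0/3 seen):

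- early: 1 - 0.343/0.373 = 0.081;
- uniform: 1 - 0.343/0.489 = 0.299.

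| Spacing | P(0/3 seen) | P(later DLT, given 0/3 seen) | P(at most 1 of 6 seen) |
|---|---|---|---|
| Complete follow-up | 34% | 0 | 42% |
| Fastest permitted | 37% to 49% | 8% to 30% | 44% to 52% |
| 15 per year, even | 35% to 37% | 2% to 7% | 42% to 44% |
| 10 per year, even | 34% | 0 | 42% |

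The last column is the MTD criterion applied to six patients. It is not the chance of escalating from level -1 after six, which first requires exactly 1 of 3; with complete follow-up that path has probability 3 x 0.3 x 0.49 x 0.343 = 15%.

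**The case against.** **A coherent reading exists.** One can hold that no patient is free of DLT until day 30, so the 0-of-3 condition already implies a full window and the 14 days is only an extra floor. The floor would still have a use when moving down from level 1. But the text does not say this, and on that reading the 14 days could never matter for escalation. Two teams could both follow the protocol and act differently.

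**Manufacturing takes time.** Leukapheresis must precede infusion by at least 21 days (3.1.2), so a level 1 infusion on day 28 needs a patient collected by day 7. Nothing forbids such a queue, and section 3.1.3 says: "Cell products may be cryopreserved during production to accommodate patient treatment schedules". If collection waits until the third infusion on day 14, level 1 starts on day 35 at the earliest. Follow-up is then 35, 28 and 21 days, and two of 3 are still incomplete. P(0/3 seen) becomes 36% to 40%, and the chance of a later DLT 3% to 14%. The gap shrinks but remains.

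**The margin is thin.** The result of none complete turns on 28 against 30 days. At 8-day spacing the first patient reaches day 30, leaving two of 3 and two of 6 incomplete. This stands as a limit on the headline count.

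**The assumed rate may be high.** The earlier E6 TCR trial (1.2.6) reports no cell-related DLT in 12 patients, for a one-sided 95% upper bound of 1 - 0.05^(1/12) = 22%; its DLT definition is not given. At a 10% rate the chance of a later DLT at the fastest spacing is 2% to 9%. Uniform onset is also unfavourable for one infusion plus at most two aldesleukin doses. These points lower the illustration and leave the mismatch between sections untouched.

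**Accrual is slow.** This is true on average, and at 10 per year with even gaps there is no shortfall. Real gaps vary, however, and infusions can cluster.

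**Conclusion.** The concern holds. The protocol defines a DLT over 30 days and permits dose decisions on less, with no text that closes the difference. That conclusion is calendar arithmetic on the protocol's own figures and needs no assumption about toxicity.

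Its practical size depends on spacing. At the permitted minimum, none of 3 patients, or three of 6, has a complete window. At the upper end of the stated accrual with even gaps, one patient is about 6 days short (30 - 24.3). At the lower end nothing is lost. The probabilities rest on the assumed 30% rate and the two onset patterns, and show direction and rough scale only.

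I would treat it as a required correction even though the worst case is not the expected one. It concerns the rule behind the primary result, the exposure at stake is tenfold and irreversible, and the remedy is small.

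**What to change.** Reconcile sections 3.1.5 and 3.1.6, together with the Cohort 2 entry in 2.3.1 and section 7.5.1. The decision to escalate, the declaration of the MTD and the opening of Cohort 2 should all rest on the same observation window that defines a DLT. State the follow-up each counted patient must have at each of those decisions. Which figure governs is for the sponsor to decide.

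The cost is one or two sentences by amendment. If the 30-day window is the one kept, each transition waits up to 30 - 14 = 16 days longer at the fastest spacing: the earliest next infusion moves from day 28 to day 44 after three patients, and from day 49 to day 65 after six. The added wait is about 6 days at 15 per year and none at 10 per year. The 12 and 18 patients do not change.

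A minor drafting point can go in the same amendment. The month-1 visit window is +/- 7 days in section 3.5 but +/- 14 days in footnote 9 of the study calendar. Adverse event collection continues after that visit, so this does not cut short the capture of DLTs, but the two should agree.

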### 3.1.7 Safety Protocol Stopping Rules

The study may be halted if any of the following safety conditions are met:

1. If one or more deaths occur, we will immediately stop accrual and promptly discuss this with the NCI IRB and the FDA.
2. If two or more patients develop a Grade 3 or greater toxicity not attributable to the aldesleukin (or circumstances unrelated to the study) that does not resolve to Grade 2 within 24 hours.
3. If two patients develop Grade 3 or greater Immune Related Adverse Event (IRAE) related to aldesleukin that cannot be resolved to less than or equal to a Grade 2 within 10 days.
4. If 2 DLTs occur on dose level 1.

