## **6.3 RESPONSE CRITERIA**

### **6.3.1 Definitions**

Evaluable for toxicity: All patients will be evaluable for toxicity from the time of E6 TCR T cell infusion. Toxicity data will be collected for all patients.

Evaluable for objective response: Only those patients who have measurable disease present at baseline, have received an E6 TCR T cell infusion, and have had their disease re-evaluated for response will be considered evaluable for response. These patients will have their response classified according to the definitions stated below.

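### Section 3.1.6 accepts doses within 30% of target, yet drops from the MTD decision, DLTs included, any patient whose product is short of target

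*Combined protocol and SAP*

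**What the plan says.** Section 3.1.6 sets targets of 0.7 x 10^10 transduced T cells (level -1) and 0.7 x 10^11 (level 1), and defines the MTD as the highest level with no more than one DLT in six patients. On the dose actually given it says: "The cell dose administered will be in a range of +/- 30% of the target dose above". Later in the same paragraph it deals with products that do not reach the target number. The patient is treated, but "toxicity data from the patient will not be used in determining the MTD, and that patient will be replaced in the protocol enrollment". There is no exception for DLTs, and the shortfall is not tied to the 30% range.

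Four other places bear on who is counted:

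- Section 3.1.5 sets no cell-dose condition for a DLT: "All treatment related Grade 3 and greater AEs occurring within 30 days of the cell infusion will be considered DLTs", apart from listed transient aldesleukin effects.
- Section 3.1.7 opens with "The study may be halted if any of the following safety conditions are met", and its fourth condition reads "If 2 DLTs occur on dose level 1". It does not say whether patients excluded under 3.1.6 count. Conditions 1 to 3 carry no cell-dose limit.
- Section 7.5.1 says "Decisions about dose level enrollment and dose escalation if applicable will be made based on the toxicity data from prior patients".
- Section 8 allows extra enrolment for "patients who enroll but are not evaluable for the primary endpoint" without defining them.

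**The concern.** The two sentences in 3.1.6 use the target differently. The first treats it as the centre of an accepted range. The second, taken at its word, treats it as a floor. A product between 70% and 100% of target passes the first and fails the second. If the second sentence means the lower limit of the range, the two agree, but the text does not say so.

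The design turns on one or two events among three or six patients, so who is counted decides the primary result. Under the literal reading the counted patients are those at 100% to 130% of target. A DLT in a patient at, say, 80% of target disappears from the MTD decision and a new patient takes her place. The same happens to a DLT in a patient below the range. Yet a DLT at a lower cell dose gives no reassurance about a higher one.

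**Working it through.** **The plan's own figures.** Two levels of six give 2 x 6 = 12 patients for the MTD, and six more at the MTD give 12 + 6 = 18. Both match section 8. They count evaluable patients only, so the exclusion does not change them. The plan gives no pass probabilities.

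**The overlap.** Using the targets and the 30% range in 3.1.6:

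- Level -1: 0.7 x 0.7 = 0.49 and 1.3 x 0.7 = 0.91, so the range is 0.49 to 0.91 x 10^10. Products from 0.49 to just under 0.70 x 10^10 are in range but short of target.
- Level 1: the same with 10^11.

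**A possible outcome.** One DLT among six counted patients, plus one in a replaced patient, is two DLTs in seven treated. The level still meets the limit of one in six.

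**Assumptions for size.** The documents give neither the number of short products nor their DLT risk. I take one short-product patient, with risk p for counted patients and q for her. If she has no DLT she is replaced. The comparison is between leaving her DLT out and letting it count as one of the level's patients.

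**Level 1, at most one DLT in six.**

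- Not counted: P = (1-p)^6 + 6p(1-p)^5.
- Counted: (1-q)P + q(1-p)^5. If she has a DLT, the other five must have none.
- p = q = 1/3: P = 0.0878 + 0.2634 = 0.351. Counted: 0.6667 x 0.3512 + 0.3333 x 0.1317 = 0.278. Fall: 7.3 points.
- p = q = 1/6: P = 0.3349 + 0.4019 = 0.737. Counted: 0.8333 x 0.7368 + 0.1667 x 0.4019 = 0.681. Fall: 5.6 points.
- If the short product carries less risk (p = 1/3, q = 1/6): 0.8333 x 0.3512 + 0.1667 x 0.1317 = 0.315. Fall: 3.7 points. With q = 0 there is no fall.

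**Level -1, chance of escalating.** Two further assumptions are needed: that the MTD exclusion also governs escalation, and that she is among the first three patients.

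- Not counted: E = (1-p)^3 + 3p(1-p)^5.
- Counted: (1-q)E + q(1-p)^5.
- p = q = 1/3: E = 0.2963 + 0.1317 = 0.428. Counted: 0.6667 x 0.4280 + 0.3333 x 0.1317 = 0.329. Fall: 9.9 points.
- p = q = 1/6: E = 0.5787 + 0.2009 = 0.780. Counted: 0.8333 x 0.7796 + 0.1667 x 0.4019 = 0.717. Fall: 6.3 points.

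The stopping conditions in 3.1.7 are not modelled. If condition 4 covers all infused patients and is acted on, a level 1 pass with two or more DLTs among treated patients cannot occur.

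**The case against.** The best defence is that the exclusion is narrow and most of the surrounding text is sound. Much of that stands.

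- **A reader might infer that several sections contradict 3.1.6.** They do not. Section 3.1.5 says which events are DLTs. Section 6.3.1 ("All patients will be evaluable for toxicity from the time of E6 TCR T cell infusion. Toxicity data will be collected for all patients") governs collection and reporting. Section 7.5.1 describes how the team decides on escalation. A patient can be evaluable for toxicity and not for the MTD.
- **A reader might infer that the exclusion also controls escalation.** Section 3.1.6 words it only for determining the MTD, and 7.5.1 has no such exclusion. The level -1 figures therefore depend on an assumption.
- **A reader might infer that a patient could be reclassified after her outcome.** Appendix D makes viable cell number and TCR expression available at infusion, so her count is fixed beforehand. Only the meaning of the cut-off is open.
- **A reader might infer that short products are common.** The Appendix D limits (more than 1 x 10^9 viable cells, more than 10% TCR positive) could be met by little more than 1 x 10^8 transduced cells, 70-fold below the level -1 target. That is a release floor, not an expected yield. Section 3.1.3 retains cells for three productions, so shortfalls may be rare.
- **Safety is still watched.** Conditions 1 to 3 in 3.1.7 could halt the study whatever the cell dose. They do not cover every DLT, however, and condition 4 applies to level 1 only, is permissive, and is silent on excluded patients.
- **Replacing a short-product patient who has no DLT is defensible.** The exclusion does not by itself bias the 3+3 at the target dose, and counting below-range patients only when they have a DLT would not give an unbiased rate.

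None of this settles whether an in-range patient below 100% of target counts, or what happens to a DLT below the range.

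**Conclusion.** Section 3.1.6 is wrong as written, in a limited way. Followed literally, it removes from the MTD decision patients whose dose the same paragraph accepts, together with their DLTs. It also removes any DLT below the range, without saying whether that DLT counts for escalation or for condition 4. A level can therefore be declared tolerable with two or more DLTs among treated patients.

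The size cannot be known from the documents. With one short product and equal risk for all, counting its DLT changes the level 1 pass rate by 7.3 points at risk 1/3 and by 5.6 points at risk 1/6. For escalation from level -1, under the two further assumptions, the changes are 9.9 and 6.3 points. A lower risk with the short product shrinks the effect, and if no product falls short there is none. The firm part is the overlap between range and exclusion, which rests on the text and needs no assumed rate.

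**What to change.** 1. In section 3.1.6, tie the exclusion to a single boundary consistent with the 30% range. Apply it from the release cell count before outcomes are known, so that in-range patients and their DLTs count for the MTD.
2. Reconcile 3.1.6 with condition 4 of 3.1.7 by stating whether a DLT in a below-range patient counts toward the MTD, toward escalation and toward that condition. The sponsor decides the rule. Use the same definition for patients not evaluable for the primary endpoint in section 8.
3. Report DLT counts at each level for in-range patients and, separately, for all infused patients.

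The cost is protocol wording and one more table. If the sponsor chooses to count below-range DLTs, a level will be stopped somewhat more often, including when its true risk is acceptable. The risk 1/6 results above show the scale of that.
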